6.2 Subject Exclusion Criteria

Patients who meet any of the following criteria will be excluded from study entry.

General Exclusion Criteria:

Follicular lymphoma grade 3B

Concurrent aggressive non-Hodgkin lymphoma (eg, diffuse large B cell lymphoma [DLBCL])

Any anticancer therapy, including chemotherapy, hormonal therapy, investigational therapy, or radiotherapy, within 3 weeks, or 5 half lifes, whichever is shortest, prior to initiation of study treatment. However, the following are allowed:

- Hormone-replacement therapy or oral contraceptives
- Herbal therapy, provided it is discontinued at least 1 week prior to Cycle 1, Day 1
- Palliative radiotherapy for bone metastases, provided most recent fraction not given within 2 weeks of Cycle 1, Day 1 and most recent fraction was not administered to planned area of radiation while on study.

AEs from prior anticancer therapy that have not resolved to Grade \leq 1, with exception of alopecia or skin/nail hyperpigmentation.

Bisphosphonate therapy for symptomatic hypercalcemia within 2 weeks of cycle 1, day 1

- Use of bisphosphonate therapy for other reasons (e.g., bone metastasis or osteoporosis) is allowed. Denosumab should not be used while on therapy (see section 9.2.2)

Known clinically significant liver disease, including active viral, alcoholic, or other hepatitis; cirrhosis; fatty liver; and inherited liver disease

Active central nervous system (CNS) involvement of lymphoma.

- Patients with a history of CNS involvement of lymphoma are eligible, provided they received treatment greater than 30 days prior to cycle 1 day 1 and there is no evidence of involvement on most recent assessment.

Pregnant or breastfeeding, or intention of becoming pregnant during study treatment or within 5 month after the final dose of study treatment.

- Women of childbearing potential must have a negative serum pregnancy test result within 30 days prior to initiation of study treatment.

Known hypersensitivity to Chinese hamster ovary cell products, other recombinant human antibodies, or to any component of the atezolizumab formulation.

Inability to comply with study and follow-up procedures

Active or history of autoimmune disease, including but not limited to myasthenia gravis, myositis, autoimmune hepatitis, systemic lupus erythematosus, rheumatoid arthritis, inflammatory bowel disease, vascular thrombosis associated with antiphospholipid syndrome, Wegener's granulomatosis, Sjögren's syndrome, Bell's palsy, Guillain-Barré syndrome, multiple sclerosis, autoimmune thyroid disease, vasculitis, or glomerulonephritis

- Patients with a history of autoimmune hypothyroidism on a stable dose of thyroid replacement hormone may be eligible.
- Patients with controlled Type 1 diabetes mellitus on a stable insulin regimen may be eligible.
- Patients with inactive inflammatory bowel disease, not currently receiving therapy, may be eligible.

- Patients with eczema, psoriasis, lichen simplex chronicus or vitiligo with dermatologic manifestations only (e.g., patients with psoriatic arthritis would be excluded) are permitted provided that they meet the following conditions:

- Rash must cover less than 10% of body surface area (BSA)
- Disease is well controlled at baseline and only requiring low potency topical steroids (e.g., hydrocortisone 2.5%, hydrocortisone butyrate 0.1%, flucinolone 0.01%, desonide 0.05%, aclometasone dipropionate 0.05%)
- No acute exacerbations of underlying condition within the last 12 months (not requiring psoralen plus ultraviolet A radiation [PUVA], methotrexate, retinoids, biologic agents, oral calcineurin inhibitors; high potency or oral steroids)

History of idiopathic pulmonary fibrosis, pneumonitis (including drug induced), organizing pneumonia (i.e., bronchiolitis obliterans, cryptogenic organizing pneumonia, etc.), or evidence of active pneumonitis on screening chest computed tomography (CT) scan

- History of radiation pneumonitis is permitted provided patient is asymptomatic and did not require systemic or inhaled corticosteroids for treatment of symptomatic radiation pneumonitis.

Any other diseases, metabolic dysfunction, physical examination finding, or clinical laboratory finding giving reasonable suspicion of a disease or condition that contraindicates the use of an investigational drug or that may affect the interpretation of the results or render the patient at high risk from treatment complications

History of HIV infection or active hepatitis B (chronic or acute) or hepatitis C infection

- Patients with past or resolved hepatitis B infection (defined as having a negative hepatitis B surface antigen [HBsAg] test and a positive anti-HBc [antibody to hepatitis B core antigen] antibody test) are eligible.
- Patients positive for hepatitis C virus (HCV) antibody are eligible only if polymerase chain reaction (PCR) is negative for HCV RNA.

Active tuberculosis

Severe infections within 4 weeks prior to Cycle 1, Day 1, including but not limited to hospitalization for complications of infection, bacteremia, or severe pneumonia

Major surgical procedure within 28 days prior to Cycle 1, Day 1 or anticipation of need for a major surgical procedure during the course of the study

Administration of a live, attenuated vaccine within 4 weeks before Cycle 1, Day 1, within 5 months after the final dose, or anticipation that such a live, attenuated vaccine will be required during the study

- Influenza vaccination should be given during influenza season only (approximately October to March). Patients must not receive live, attenuated influenza vaccine (e.g., FluMist[®]) within 4 weeks prior to Cycle 1, Day 1 or at any time during the study.

Malignancies other than the disease under study within 3 years prior to Cycle 1, Day 1, with the exception of those with a negligible risk of metastasis or death and with expected curative

outcome (such as adequately treated carcinoma in situ of the cervix, basal or squamous cell skin cancer, localized prostate cancer treated surgically with curative intent, or ductal carcinoma in situ treated surgically with curative intent) or undergoing active surveillance per standard-of-care management (e.g., chronic lymphocytic leukemia Rai Stage 0, prostate cancer with Gleason score ≤ 6 , and prostate-specific antigen [PSA] ≤ 10 mg/mL, etc.)

Medication Related Exclusion Criteria

Prior treatment with anti-PD-1, or anti-PD-L1 therapeutic antibody or pathway-targeting agents. Patients who have received prior treatment with anti-CTLA-4 may be enrolled, provided the following requirements are met:

- Minimum of 12 weeks from the first dose of anti-CTLA-4 and > 6 weeks from the last dose
- No history of severe immune-related adverse effects from anti-CTLA-4 (NCI CTCAE Grade 3 and 4)

Treatment with systemic immunostimulatory agents (including but not limited to interferon [IFN]- α or interleukin [IL]-2) within 6 weeks or five half-lives of the drug (whichever is shorter) prior to Cycle 1, Day 1

Treatment with systemic immunosuppressive medications (including but not limited to prednisone, cyclophosphamide, azathioprine, methotrexate, thalidomide, and anti-tumor necrosis factor [anti-TNF] agents) within 1 week prior to Cycle 1, Day 1

- Patients who have received acute, low-dose, systemic immunosuppressant medications (e.g., a one-time dose of dexamethasone for nausea or prednisone for intravenous contrast allergy) may be enrolled.
- Palliative systemic steroids for palliation of disease are allowed but must be discontinued at least 7 days prior to cycle 1, day 1
- The use of inhaled corticosteroids and mineralocorticoids (e.g., fludrocortisone) for patients with orthostatic hypotension or adrenocortical insufficiency is allowed.

History of severe allergic, anaphylactic, or other hypersensitivity reactions to chimeric or humanized antibodies or fusion proteins

Patients with prior allogeneic bone marrow transplantation or prior solid organ transplantation

7.0 RECRUITMENT PLAN

Potential research subjects will be identified by a member of the patient's treatment team, the protocol investigator, or research team. If the investigator is a member of the treatment team s/he will screen their patient's medical records for suitable research study participants and discuss the study and their potential for enrolling in the research study. Furthermore, eligible patients from the lymphoma services will be identified by investigators at the time of medical disciplinary rounds or in clinic at Memorial Sloan Kettering Cancer Center.

8.0 PRETREATMENT EVALUATION

Pretreatment evaluations will be performed according to study flowchart in Appendix 1.

9.0 TREATMENT/INTERVENTION PLAN

9.1 Atezolizumab administration

Atezolizumab will be administered on an every 21-day (+/-2 days) dosing schedule. Atezolizumab will be initiated at 1200mg IV for a planned total of 17 cycles of therapy. Dose modification or treatment interruption/discontinuation may occur as described in section 9.2.

For patients assigned to receive atezolizumab and low-dose radiotherapy, 4Gy will be administered in 2 fractions, on days 2 and 3 of cycle 1, to a single nodal site amenable to radiation as identified by the radiation oncologist (see section 5.2).

9.2 Concomitant and Excluded Therapies

9.2.1 Concomitant Therapy

Concomitant therapy includes any prescription medications or over-the-counter preparations used by a patient between the 14 days preceding the screening evaluation and the treatment discontinuation visit.

Patients who experience infusion-associated symptoms may be treated symptomatically with acetaminophen, ibuprofen, diphenhydramine, and/or cimetidine or another H2 receptor antagonist, as per standard practice (for sites outside the United States, equivalent medications may be substituted per local practice). Serious infusion-associated events manifested by dyspnea, hypotension, wheezing, bronchospasm, tachycardia, reduced oxygen saturation, or respiratory distress should be managed with supportive therapies as clinically indicated (e.g., supplemental oxygen and β_2 -adrenergic agonists).

Systemic corticosteroids and Con TNF α inhibitors may attenuate potential beneficial immunologic effects of treatment with ATEZOLIZUMAB but may be administered at the discretion of the treating physician. If feasible, alternatives to corticosteroids should be considered. Premedication may be administered for Cycles ≥ 2 at the discretion of the treating physician. The use of inhaled corticosteroids and mineralocorticoids (e.g., fludrocortisone) for patients with orthostatic hypotension or adrenocortical insufficiency is allowed. Megastrol administered as appetite stimulant is acceptable while the patient is enrolled in the study.

Patients who use oral contraceptives, hormone-replacement therapy, prophylactic or therapeutic anticoagulation therapy (such as low-molecular-weight heparin or warfarin at a stable dose level), or other allowed maintenance therapy (see Section 6.2) should continue their use. Males and females of reproductive potential should use highly effective means of contraception.

9.2.2 Excluded Therapy

Any concomitant therapy intended for the treatment of cancer, whether health authority approved or experimental, is prohibited. This includes but is not limited to the following:

G-CSF solely to maintain the ANC and not associated with the treatment of a documented or suspected infection in the setting of febrile neutropenia

Chemotherapy, hormonal therapy, immunotherapy, radiotherapy, investigational agents, or herbal therapy

Traditional herbal medicines should not be administered because the ingredients of many herbal medicines are not fully studied and their use may result in unanticipated drug-drug interactions (DDIs) that may cause or confound assessment of toxicity.

The following therapies are excluded while patients are receiving atezolizumab and for 10 weeks after the last dose of atezolizumab:

Patients who are receiving a RANKL inhibitor (denosumab) prior to enrollment must be willing and eligible to receive a bisphosphonate instead; denosumab could potentially alter the activity and the safety of atezolizumab.

Patients are not allowed to receive immunostimulatory agents, including but not limited to IFN- α , IFN- γ , or IL-2. These agents, in combination with atezolizumab, could potentially increase the risk for autoimmune conditions.

Patients should not receive other immunostimulatory agents for 10 weeks after the last dose of atezolizumab.

Patients should not receive immunosuppressive medications, including but not limited to cyclophosphamide, azathioprine, and methotrexate. These agents could potentially alter the activity and the safety of atezolizumab. Systemic corticosteroids and anti TNF agents may attenuate potential beneficial immunologic effects of treatment with atezolizumab but may be administered at the discretion of the treating physician. If feasible, alternatives to these agents should be considered.

Patients must not receive live, attenuated influenza vaccine (e.g., FluMist[®]) within 4 weeks prior to Cycle 1, Day 1 or at any time during the study. Inactivated vaccines are allowed.

In addition, the investigator should contact the Medical Monitor if questions arise regarding medications not listed above.

9.3 Guidelines for Dosage Modification and Treatment Interruption or Discontinuation

ATEZOLIZUMAB treatment will be given as long as the patient continues to experience clinical benefit in the opinion of the investigator until the earlier of unacceptable toxicity, symptomatic deterioration attributed to disease progression, or any of the other reasons for treatment discontinuation listed in Section 13.1.

There will be no dose reduction for ATEZOLIZUMAB in this study. Patients may temporarily suspend study treatment for up to 42 days beyond the scheduled date of delayed infusion if study drug-related toxicity requiring dose suspension is experienced. If ATEZOLIZUMAB is held because

of AEs for >42 days beyond the scheduled date of infusion, the patient will be discontinued from ATEZOLIZUMAB and will be followed for safety and efficacy as specified in Section 10.2 and 10.3.

If a patient must be tapered off steroids used to treat AEs, ATEZOLIZUMAB may be held for additional time beyond 42 days from the scheduled dose until steroids are discontinued or reduced to a prednisone dose (or dose equivalent) of ≤ 10 mg/day. The acceptable length of interruption will be at the discretion of the investigator.

Dose interruptions for reasons other than toxicity, such as surgical procedures, may be allowed. The acceptable length of interruption will be at the discretion of the Principal Investigator.

Any toxicities associated or possibly associated with ATEZOLIZUMAB treatment should be managed according to standard medical practice. Additional tests, such as autoimmune serology or biopsies, may be used to determine a possible immunogenic etiology. Although most irAEs observed with immunomodulatory agents have been mild and self-limiting, such events should be recognized early and treated promptly to avoid potential major complications. Discontinuation of ATEZOLIZUMAB may not have an immediate therapeutic effect, and there is no available antidote for ATEZOLIZUMAB. In severe cases, immune-related toxicities may be acutely managed with topical corticosteroids, systemic corticosteroids, or other immunosuppressive agents.

Patients should be assessed clinically (including review of laboratory values) for toxicity prior to, during, and after each infusion. If unmanageable toxicity due to ATEZOLIZUMAB occurs at any time during the study, treatment with ATEZOLIZUMAB should be discontinued.

10.0 EVALUATION DURING TREATMENT/INTERVENTION

10.1 Study Assessments

The flowchart of scheduled study assessments is provided in Appendix 1.

Patients will be closely monitored for safety and tolerability throughout the study. All assessments must be performed and documented for each patient.

10.1 Laboratory/ Pathology Assessments

Samples for hematology, serum chemistries, coagulation, urinalysis, and the pregnancy test will be analyzed at the study site's local laboratory. Analysis of biomarkers on tumor and blood samples will be performed on site. Refer to section 12.2 and Appendix 9 for correlative studies workflow.

The following assessments will be performed at Memorial Sloan-Kettering Cancer Center:

Baseline tumor biopsy

- All patients will undergo a baseline tumor biopsy sample collection within 30 days of registration.
 - If the patient has recently undergone a biopsy and has not received any intercurrent anti-lymphoma therapy, archival tissue can be used

- Acceptable samples include core needle biopsies for deep tumor tissue or lymph nodes or excisional, incisional, punch, or forceps biopsies for cutaneous, subcutaneous, or mucosal lesions.
- Every intention should be made to collect the pre treatment biopsy from the same site that will be radiated. The on protocol biopsy should be in the same location unless clinically unfeasible or not in the interest of the patient's safety.

On-treatment tumor biopsy

- All patients will undergo an on-treatment tumor biopsy sample collection, if clinically feasible, during Cycle 2 (as per study flowchart in Appendix 1).
- Acceptable samples include fine needle aspirations or core needle biopsies for deep tumor tissue or lymph nodes or excisional, incisional, punch, or forceps biopsies for cutaneous, subcutaneous, or mucosal lesions. Core needle biopsies are preferred.
- The tissue will be used for correlative investigations.

Tumor biopsy at the time of initial radiographic progression (This tumor biopsy is **optional** based on whether it is feasible to obtain enough tissue at the site and therefore, 'clinically indicated/feasible', and not optional for the patient to choose whether or not they want one for the study)

- Patients may undergo a tumor biopsy sample collection, if clinically feasible, at the first evidence of early radiographic disease progression (i.e., not preceded by meaningful tumor regression). Biopsy at time of initial radiographic progression is recommended but not mandatory.
- Acceptable samples include fine needle aspirations or core needle biopsies for deep tumor tissue or lymph nodes or excisional, incisional, punch, or forceps biopsies for cutaneous, subcutaneous, or mucosal lesions.
- If CT-guided is necessary for the investigational on-treatment biopsy, the average tissue radiation dose resulting from CT-guided biopsy procedures is 4.56 mGy.

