6.0 CRITERIA FOR SUBJECT ELIGIBILITY

6.1 Subject Inclusion Criteria

Patients must meet the following criteria for study entry:

Signed Informed Consent Form (ICF)

Ability and willingness to comply with the requirements of the study protocol.

Age ≥ 18 years

Relapsed or refractory follicular lymphoma grade 1, 2, or 3A

- Relapsed disease is defined as having relapsed after greater than 6 months of prior treatment for follicular lymphoma
- Refractory disease is defined as failure to achieve a complete response or relapsed within 6 months of treatment for follicular lymphoma

Pretreatment biopsy for fresh tumor tissue collection is required

- If patient has recently undergone a biopsy and has not received any intercurrent anti-lymphoma therapy, archival tissue can be used

Stage III/IV disease

- Stage II disease is also eligible if disease is not encompassable within a single radiation field, as determined by the radiation oncologist.

At least one prior treatment for follicular lymphoma (no restriction to number or type of prior therapies)

- Patients treated for transformed diffuse large B cell lymphoma (DLBCL) who have retrograde transformation are eligible provided they have received at least one prior treatment for the follicular lymphoma

Site of disease amenable to low-dose, local radiotherapy (2 \times 2Gy), as recommended by the radiation oncologist.

At least one bi-dimensionally measurable lesion > 1.5 cm in its *longest diameter* by CT scan or magnetic resonance imaging as defined by the *Lugano Classification*

Adequate hematologic and end organ function:

- ANC ≥ 1500 cells/ μ L
 - If there is documented bone marrow involvement of follicular lymphoma, ANC must be ≥ 1000 cells/ μ L
- Platelet count $\geq 75,000$ μ L
 - If there is documented bone marrow involvement of follicular lymphoma, platelet count must be $\geq 50,000$ μ L
- Hemoglobin ≥ 9.0 g/dL
 - If there is documented bone marrow involvement of follicular lymphoma, hemoglobin must be ≥ 8.0 g/dL
- Total bilirubin $\leq 1.5 \times$ upper limit of normal (ULN)
 - Patients with known Gilbert disease who have serum bilirubin level $\leq 3 \times$ ULN may be enrolled.

- AST and ALT $\leq 3.0 \times$ ULN
 - Patients with liver involvement: AST and/or ALT $\leq 5 \times$ ULN
- Alkaline phosphatase $\leq 3 \times$ ULN
 - Patients with documented liver involvement or bone metastases: alkaline phosphatase $\leq 5 \times$ ULN

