12.0 CRITERIA FOR THERAPEUTIC RESPONSE/OUTCOME ASSESSMENT

12.1 Tumor and Response Evaluation

Any evaluable or measurable disease must be documented at screening and reassessed at each subsequent tumor evaluation. Irradiated sites of disease, previously irradiated lesions, or lesions that are intended to be used to collect tissue samples for biopsy should not be counted as target lesions. Response will be assessed by the investigator per the *Lugano Classification* (Cheson et al, 2014; see Appendix 4) at tumor assessment timepoints (see Appendix 5).

Site of disease deemed amenable to low-dose, local radiotherapy (2 x 2Gy) should not be counted as target lesions.

Previously irradiated lesions should not be counted as target lesions.

Lesions that are intended to be used to collect tissue samples for biopsy should not be counted as target lesions.

Bone lesions should not be counted as target lesions.

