20.1 Appendix 1**Flowsheet**

| | Screening | Cycle 1 | Low-dose radiotherapy | Cycle 2 | | Treatment Visits | Treatment Visits | Follow Up Visits | Off Treatment Visit |
|---|---|---------|-----------------------|--------------------|-----------|---|--|------------------------------|---------------------|
| | within 30 days of C1D1 unless otherwise specified | Day 1 | Cycle 1, Day 2 and 3 | Day 1 (+/- 2 days) | Day 14-20 | Cycle 3, 4, 6, 7, 8, 10, 11, 12, 14, 15, 16: Day 1 (+/- 2 days) | Cycle 5, 9, 13, 17: Day 1 (+/- 2 days) | Every 6 Months (+/- 14 days) | |
| Informed consent ^L | X | | | | | | | | |
| Medical history and demographics | X | | | | | | | | |
| Physical examination, including vital signs ^a , height, weight, and performance status | X | X | | X | | X | X | X | X |
| Adverse events | X | X | | X | | X | X | X | X |
| Concomitant medications | X | X | | X | | X | X | X | X |

| | | | | | | | | | |
|--|----------------|----------------|--|----------------|--|-----------------|----------------|----------------|----------------|
| Bone marrow biopsy & aspirate | X ^d | | | X ^d | | X ^d | X ^d | X ^d | X ^d |
| CBC w/ differential ^b | X | X ⁱ | | X ⁱ | | X ⁱ | X ⁱ | X | X |
| Chemistry panel ^c | X | X ⁱ | | X ⁱ | | X ⁱ | X ⁱ | X | X |
| TSH | X | X ⁱ | | X ⁱ | | X ⁱ | X ⁱ | X | X |
| Creatinine phosphokinase | X | X ⁱ | | X ⁱ | | X ⁱ | X ⁱ | X | X |
| PTT and PT/INR | X | | | | | | | | |
| Urinalysis | X | | | | | | | | |
| Infectious disease testing ^k | X | | | | | | | | |
| Pregnancy test (urine or blood) ⁿ | X ⁿ | | | | | | | | |
| Tumor Assessment | X ^e | | | | | X ^{em} | X ^e | X ^e | X ^e |
| Tumor biopsy | X ⁱ | | | X ⁱ | | | | | X ⁱ |
| Research blood samples | X ^g | | | X ^g | | X ^g | X ^g | X ^g | X ^g |

| | | | | | | | | | |
|-------------------------------------|---|--|----------------|--|--|--|--|--|---|
| Radiation oncology consultation | X | | | | | | | | |
| Low- dose radiotherapy ^h | | | X ^h | | | | | | |
| Electrocardiogram | X | | | | | | | | X |

^a Heart rate, systolic and diastolic blood pressure while the patient is in a seated position, and temperature.

^b Hemoglobin, hematocrit, platelet count, RBC count, WBC count, percent and absolute differential count (neutrophils, bands, eosinophils, lymphocytes, monocytes, basophils, other cells).

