^c Sodium, potassium, chloride, bicarbonate, glucose, BUN, creatinine, calcium, total and direct bilirubin, total protein, albumin, ALT, AST, alkaline phosphatase, amylase, lipase, LDH, uric acid, magnesium, phosphorus.

^d Bone marrow biopsy and aspirate is required within 60 days of C1D1, provided no treatment has been administered in the interim. For patients with involvement of follicular lymphoma at baseline, repeat testing is required only to confirm CR or as clinically indicated.

^e Imaging and reporting requirements for tumor assessment is described in Appendix 5. Patients will require a PET scan with diagnostic quality CT CAP (with intravenous and oral contrast, unless contraindicated) at study screening, Cycle 5, and EOT. A baseline PET with diagnostic CT CAP scan is required within 45 days of C1D1. For patients who have had a PET scan performed within 45 days of C1D1, a simulation scan (PET, CT, or MRI) will only be done if the patient is randomized to Arm 2 (RT arm). For patients who have not had a PET scan within 45 days of C1D1, baseline PET imaging will be a PET-simulation scan.

^f Tumor biopsy is required in all patients within 45 days of C1D1. Tumor FNA or core biopsy is required in all patients at Cycle 2 Days 14-20 (core biopsy is preferred). Tumor biopsy is recommended at time of progression on study. Tumor biopsy should be outside the field of radiation to allow for an accurate assessment of systemic changes to the tumor microenvironment following local irradiation. Acceptable samples include core needle biopsies for deep tumor tissue or lymph nodes or excisional, incisional, punch, or forceps biopsies for cutaneous, subcutaneous, or mucosal lesions

^g Research blood samples will be collected for correlative investigations as outlined in Section 12.2 of the protocol. Additional information about the workflow for correlatives can be found in Appendix 9.

^h Only if randomized to low- dose radiotherapy arm

ⁱ T3 and T4 should be tested only if TSH is abnormal.

- ^j Labs can be done within 5 days of day 1 of each cycle.
- ^k Infectious disease testing includes: Epstein-Barr virus (EBV) serology (EBNA IgG), Hepatitis B virus (HBV) serology (HBsAg, antibodies against HBsAg, hepatitis B core antigen), HCV serology (anti-HCV), and HIV 1 & 2 antibodies. HBV DNA test is required for patients who have positive serology for anti-HBc. HCV RNA test is required for patients who have positive serology for anti-HCV.
- ^l Within 45 Days of C1D1

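### Two separate gaps in the exploratory correlatives: Section 10.1 and Appendix 1 disagree on where to biopsy, and Section 14.6 has no between-arm estimate of TCR or cytokine change

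*Combined protocol and SAP*

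**What the plan says.** **Biopsy site.** Section 10.1, under the baseline biopsy, states "Every intention should be made to collect the pre treatment biopsy from the same site that will be radiated". It continues: "The on protocol biopsy should be in the same location unless clinically unfeasible", with a further exception for patient safety. It also says that after a recent biopsy without intervening lymphoma treatment, "archival tissue can be used". Appendix 1, footnote f, states "Tumor biopsy should be outside the field of radiation to allow for an accurate assessment of systemic changes to the tumor microenvironment". The same footnote sets the timing: "Tumor FNA or core biopsy is required in all patients at Cycle 2 Days 14-20". RT is given on Days 2 and 3 of Cycle 1 (Sections 4.2 and 5.2.3).

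**Related rules.** Section 6.1 makes this an entry criterion for everyone: "Site of disease amenable to low-dose, local radiotherapy". Section 12.1 excludes RT-amenable sites from the target lesions, and also says "lesions that are intended to be used to collect tissue samples for biopsy should not be counted as target lesions".

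**Objectives and analysis.** Section 2.3 sets out to determine what adding RT does to TCR diversity, to clinical response and to blood cytokine/chemokine levels. Section 12.2.1 repeats the TCR aim and uses biopsy and blood T cells from before and during treatment. Section 14.6 plans three things:

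- ORR, PFS and OS by biomarker-defined group, including 2-fold TCR expansion or not;
- the same association with outcome for other biomarkers;
- a Wilcoxon signed-rank test of within-patient cytokine change.

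Treatment arm is not a factor in any of them. Section 14.1 has each arm analysed on its own.

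**The concern.** The first problem is what an RT-arm tissue pair represents. Footnote f gives its purpose as reading systemic change after local irradiation. A sample from the irradiated node cannot serve that purpose, and a pair drawn from two nodes confounds change over time with differences between lesions.

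The second problem is independent of the first. What RT adds is a between-arm question, and the trial randomises, so the contrast that isolates RT will exist in the data. As written, no planned analysis uses it for TCR or cytokines.

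At stake is the mechanistic part of the trial: whether low-dose RT adds a systemic immune effect to atezolizumab. Patients undergo an on-treatment biopsy partly for this. Site status may be hard to reconstruct later, and an arm contrast chosen after the data are seen carries less weight than one written in advance.

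**Working it through.** **1. The plan's own figures.** The documents give no sample-size or precision figure for the TCR or cytokine analyses. The primary design reproduces: with 25 patients and 9 or more responders required, the exact binomial probability is 0.047 at a 20% response rate and 0.818 at 43%, against the stated 0.05 and 0.80. Nothing below changes that rule.

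**2. Site rules side by side, RT arm.** With 21-day cycles, Cycle 2 Days 14-20 are study days 21 + 14 = 35 to 21 + 20 = 41. That is 32 to 38 days after the second fraction on Day 3, so this sample is always post-RT.

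| Which text is followed | Baseline | Cycle 2 | What the pair shows |
|---|---|---|---|
| 10.1 for both | RT site | RT site | Local change, not the systemic change footnote f wants |
| Footnote f for both | Out of field | Out of field | Systemic change, but contradicts 10.1 at baseline |
| 10.1 at baseline, f at Cycle 2 | RT site | Out of field | Two different lesions |
| Practice varies | Either | Either | A mix |

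Archival baseline tissue adds samples with no stated relation to the RT site. In the control arm there is no field, so footnote f has no meaning there unless it is defined relative to an RT-amenable site. Blood TCR and cytokines do not depend on biopsy site.

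**3. Objective against analysis.** A signed-rank test shows whether cytokines moved on treatment. Pooled over arms it carries no information on RT. Within one arm it cannot separate RT from atezolizumab or from time. Relating TCR expansion to outcome answers a different question. Material for a contrast will be collected: the Appendix 1 row "Research blood samples" is marked at screening and from Cycle 2 onward for both arms.

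**4. What an added between-arm comparison could deliver.** Inputs: n pairs per arm, with 25 from Section 14.1 as the maximum and 20 and 15 assumed; changes in SD units, assumed normal; two-sided 5%; 80% power; rank-sum efficiency 3/π.

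- Detectable difference = (1.96 + 0.842) × √(2 / (n × 3/π))
- 95% CI half-width = 1.96 × √(2 / (n × 3/π))

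| Pairs per arm | Detectable, formula | Detectable, simulated | Half-width, formula | Half-width, simulated (Hodges-Lehmann) |
|---|---|---|---|---|
| 25 | 0.81 SD | 0.84 SD | 0.57 SD | 0.59 SD |
| 20 | 0.91 SD | 0.94 SD | 0.63 SD | 0.66 SD |
| 15 | 1.05 SD | 1.12 SD | 0.73 SD | 0.78 SD |

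**5. Illustration: the added tissue comparison if site were ignored.** Assumptions: RT shifts only the irradiated node, by 1 SD; there is no systemic effect; 20 pairs per arm. If a fraction f of RT-arm samples is in-field, the apparent RT effect is f × 1 SD. In 20,000 simulated trials per setting, the rank-sum test was significant as follows.

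| In-field fraction | Apparent effect | Significant |
|---|---|---|
| 0% | 0 | 5% |
| 25% | 0.25 SD | 11% |
| 50% | 0.50 SD | 29% |
| 75% | 0.75 SD | 58% |

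At 50% in-field, the rate is 11% for a local shift of 0.5 SD and 50% for 1.5 SD. With a 1 SD shift and 50% in-field, it is 34% at 25 pairs and 22% at 15.

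**The case against.** The site conflict can be read more kindly. The same-location sentence stands under the baseline heading. The on-treatment heading gives no site rule of its own and refers to Appendix 1, where footnote f sits, although that reference is mainly about timing. Both rules are worded as recommendations, and 10.1 allows exceptions. On this reading footnote f governs Cycle 2. That is a fair reading, but it does not rescue the pair: baseline then comes from the node to be irradiated and Cycle 2 from another.

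These aims are exploratory, Section 12.2.3 describes the cytokine panel only as something that may be investigated, and nothing bars by-arm reporting. All of that stands and lowers the severity. It does not supply an analysis for an objective the protocol states. The low power also stands, and it is a reason to ask for an estimate rather than a test-driven claim. The choice of Hodges-Lehmann is one option among several.

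A reader might infer that biopsy site goes unrecorded. The documents do not show that: Section 16.1.1 lists form names, not fields. What can be said is that the plan does not state how site will be recorded or used.

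A reader might also want to exclude patients assigned after one arm has filled. The documents do not support this. Block size is not given, and with blocks of 2 or 10, which divide 50 evenly into balanced blocks, the cap never overrides the list. Excluding such patients could discard valid allocations for no gain.

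**Conclusion.** Both gaps hold, as separate and low-severity points. The site instructions disagree, and every reading except footnote f for both samples leaves RT-arm tissue local, unmatched or mixed. That remaining reading contradicts 10.1 at baseline. Section 14.6 contains no analysis of what RT adds to TCR diversity or cytokines.

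On size, a between-arm comparison would detect only about 0.8 to 1.1 SD with 25 to 15 pairs per arm, where the SD scale, normality and the two smaller pair counts are assumptions. The result is therefore an estimate with a wide interval.

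Two stronger readings should be resisted. The 11%, 29% and 58% figures might be taken as error rates of the planned analysis. They are not, because the plan contains no between-arm tissue test. They show only what the added comparison would give if site were ignored, and since RT truly changes the irradiated node in that model, a significant result is wrong only if read as systemic. Nor do the documents support extending the point to the primary endpoint or to the clinical-response part of Section 2.3: Section 14.5 gives a per-arm ORR with exact 95% intervals.

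**What to change.** **Site.** Reconcile Section 10.1 and Appendix 1, footnote f, into one rule that applies to both arms. The rule is the sponsor's choice, weighed against Section 12.1, which bars RT-amenable and biopsied lesions as targets. If the rule refers to the RT-amenable site, have the radiation oncologist name that site for every patient before randomisation; Section 6.1 requires that such a site exists but does not say that one is designated. For each sample, including archival baseline tissue, record its relation to that site and whether the pair is from the same lesion. Report tissue results by that status.

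**Contrast.** Add to Section 14.6 an exploratory between-arm estimate, with 95% CI, of change from baseline to one pre-specified on-treatment timepoint, for example the Cycle 2 blood sample and the Cycle 2 biopsy. Apply it to TCR clonality, blood and tissue separately, and to cytokines where measured. A Hodges-Lehmann difference with a rank-sum test would do. State the number of pairs per arm and that there is no multiplicity control.

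**Cost.** Wording, two recorded items per sample and a few lines of analysis, with no extra patients. An out-of-field biopsy can bar a second lesion from target status while Section 6.1 requires only one measurable lesion, so a patient with few lesions could lose a target lesion for the primary endpoint. An in-field biopsy avoids that but shows local rather than systemic change.
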